10.3.2 ANALYSIS OF THE SECONDARY ENDPOINT(S)

- To estimate overall response rate.

The response rate will be estimated using binomial theory with Wilson's method for the 95% confidence interval.

- To estimate progression-free survival.

The median progression-free survival rates will be estimated from the Kaplan-Meier curve with the 95% confidence interval obtained from Greenwood's formula.

- To estimate overall survival.

The median overall survival rates will be estimated from the Kaplan-Meier curve with the 95% confidence interval obtained from Greenwood's formula.

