2. INTRODUCTION: BACKGROUND INFORMATION AND SCIENTIFIC RATIONALE

2.1 BACKGROUND INFORMATION

Primary thyroid cancers can be classified into 3 groups according to the cells of origin: 1) follicular-cell derived carcinomas which represent 95% of all thyroid cancers and include differentiated thyroid cancers (DTC) such as papillary, follicular and poorly-differentiated thyroid carcinomas; and undifferentiated or anaplastic thyroid carcinomas; 2) parafollicular or C-cell derived carcinomas, termed medullary thyroid carcinomas (MTC) that represent around 4% of all thyroid cancers; and 3) stromal-cell derived carcinomas that represent <1% of all thyroid cancers and include tumors such as thyroid lymphoma, sarcoma or fibrosarcoma. Presently, thyroid cancer exhibits the most rapidly increasing incidence of all solid tumors in the United States and several other countries; and it is already the fifth most common cancer among women in the United States (1-5). During 2017, it is expected that 56,870 patients will be diagnosed with thyroid cancer (6). Despite this rapid increase in incidence, thyroid cancer-specific mortality has remained stable for the last 50 years and most patients with differentiated thyroid cancer have an excellent prognosis with an estimated five-year survival rate > 98% (6). Nonetheless, the five-year survival rate if distant metastases are present is considerably worse (56%), which has also remained unchanged for several decades (6).

In the last decade our understanding of the underlying genetic alterations of thyroid cancer has improved significantly, leading to the development of new therapies (7, 8). Since 2011, the FDA has approved four novel tyrosine kinase inhibitors (TKI) for the treatment of progressive metastatic thyroid cancer: Lenvatinib and Sorafenib for DTC; and Cabozantinib and Vandetanib for MTC).

Lenvatinib is an inhibitor of the vascular endothelial growth factor receptors (VEGFR) 1-3; the fibroblast growth factor receptors 1-4; the platelet-derived growth factor receptor α ; RET; and KIT. In a phase III randomized placebo controlled study (SELECT), Lenvatinib was associated with significant improvements in progression-free survival (18.3 versus 3.6 months) and response rate (64.8% versus 1.5%) (9). Sorafenib is an inhibitor of the VEGFR 1-3, RET, RAF

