3. OBJECTIVES AND PURPOSE

Primary objective:

- To evaluate the efficacy and tolerability of TKI therapy (Lenvatinib or Sorafenib for DTC; Cabozantinib or Vandetanib for MTC) through adaptive (intermittent) versus conventional (continuous) regimen.

Secondary objective:

- To evaluate response and survival of TKI therapy (Lenvatinib or Sorafenib for DTC; Cabozantinib or Vandetanib for MTC) through adaptive (intermittent) versus conventional (continuous) regimen.

Exploratory objective:

- To determine predictive biomarkers of TKI response.

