4.2.2 SECONDARY ENDPOINTS

We will evaluate overall response rate, progression free survival and overall survival of the adaptive therapy regimen and of the conventional therapy regimen.

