10. STATISTICAL CONSIDERATIONS

10.1 STATISTICAL AND ANALYTICAL PLANS

This is a randomized phase II clinical trial with 2:1 randomization to adaptive therapy versus conventional therapy. The primary endpoint is time-to-discontinuation (TTD) of treatment, which is a "survival analysis"-type statistical comparison. We plan to enroll 24 patients on the adaptive therapy and 12 on the conventional therapy arm. Assuming uniform enrollment of patients for 2 years, with a minimum follow-up of 2 years, and a one-sided $\alpha = 0.20$, we will have 82% power to detect a hazard ratio of 0.50, assuming 12 and 24 month median TTD for the conventional and adaptive therapy groups. If the median TTD of the adaptive group is 20 months (HR=0.6), the power is 67%.

We anticipate that 20% of the patients will not have the $\geq 50\%$ drop in tumor markers needed for study randomization arm of the study. Thus, we anticipate recruiting ~45 patients to have 36 patients for randomization.

The ~9 patients enrolled to the trial not candidates for the randomization will be given conventional therapy as standard of care. As an exploratory analysis, and realizing that the sample sizes are small, we will compare their PFS rates with the 12 patients from the randomized portion of the trial who receive conventional therapy using the log-rank test.

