10.4 SAMPLE SIZE

The planned study is a randomized clinical trial, with 2:1 randomization to adaptive therapy versus conventional therapy. The primary endpoint is time-to-discontinuation (TTD) of treatment, which is a “survival analysis”-type statistical comparison. We plan to enroll 24 patients on the adaptive therapy and 12 on the conventional therapy arm. Assuming uniform enrollment of patients for 2 years, with a minimum follow-up of 2 years, and a one-sided $\alpha = 0.20$, we will have 82% power to detect a hazard ratio of 0.50, assuming 12 and 24 month median TTD for the conventional and adaptive therapy groups. If the median TTD of the adaptive group is 20 months (HR=0.6), the power is 67%.

We anticipate that 20% of the patients will not have the $\geq 50\%$ drop in tumor markers needed for study randomization arm of the study. Thus, we anticipate recruiting ~45 patients to have 36 patients for randomization.

Objective time-to-discontinuation criteria are described in Section 4.2.1. Patients may electively withdraw from treatment at any time and will be counted as a discontinuation event. All randomized patients will be included in the primary analysis. A sensitivity analysis will also be conducted, where the patients who choose to withdraw are considered as censored (non-events) at the time of withdrawal.

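### Section 10.3.2 plans no adaptive-versus-conventional effect estimate for response, PFS or OS, and relies on a median that may not be reached for OS

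*Combined protocol and SAP*

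**What the plan says.** Section 3 words the secondary objective as a comparison: "To evaluate response and survival of TKI therapy (Lenvatinib or Sorafenib for DTC; Cabozantinib or Vandetanib for MTC) through adaptive (intermittent) versus conventional (continuous) regimen". Section 4.2.2 restates it arm by arm: "We will evaluate overall response rate, progression free survival and overall survival of the adaptive therapy regimen and of the conventional therapy regimen".

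Section 10.3.2 then gives one estimation method per endpoint.
- Response: "The response rate will be estimated using binomial theory with Wilson's method for the 95% confidence interval".
- PFS: "The median progression-free survival rates will be estimated from the Kaplan-Meier curve with the 95% confidence interval obtained from Greenwood's formula".
- OS: "The median overall survival rates will be estimated from the Kaplan-Meier curve", with the same kind of interval.

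The section names no hazard ratio, log-rank test, risk difference or landmark rate. It does not itself say that the estimates are by arm.

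The only between-group PFS analysis in the plan is in section 10.1. It concerns the roughly 9 enrolled patients who do not qualify for randomisation: "we will compare their PFS rates with the 12 patients from the randomized portion of the trial who receive conventional therapy using the log-rank test". The randomised comparison would have more patients. Section 10.4 says: "We plan to enroll 24 patients on the adaptive therapy and 12 on the conventional therapy arm".

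**The concern.** A comparative objective needs an estimate of the difference between the arms, with its uncertainty. Followed as written, section 10.3.2 yields two response rates, two PFS medians and two OS medians, each with its own interval, and leaves the reader to compare them by eye. The weaker, non-randomised comparison has a stated method, while the randomised one has none.

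The second issue is the choice of summary. A Kaplan-Meier median exists only if the curve falls to 50% during follow-up. If it does not, the planned OS result is that the median was not reached, and section 10.3.2 names no fallback such as a survival rate at a fixed time.

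**Working it through.** **Inputs.** Section 10.4: 24 adaptive and 12 conventional patients, 2 years of uniform accrual, minimum follow-up of 2 years. If everyone is followed to the end, each patient has 24 to 48 months. Section 2.1: median PFS on continuous therapy of 10.8, 11.2, 18.3 and 30.5 months for the four drugs, and response rates of 28% to 64.8%. Section 2.1 also gives 56% five-year survival with distant metastases. No median OS is given for the trial population.

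**The plan's own figure.** With exponential times and rate λ = ln 2 / median, expected events in an arm of n are n × [1 − (e^(−24λ) − e^(−48λ)) / (24λ)].
- Median 12, n = 12: 12 × [1 − (0.25 − 0.0625)/1.386] = 10.4.
- Median 24, n = 24: 24 × [1 − (0.50 − 0.25)/0.693] = 15.3.
- SE of the log hazard ratio = √(1/10.4 + 1/15.3) = 0.402. Power at one-sided 0.20 = Φ(0.693/0.402 − 0.842) = 81%, against the stated 82%.
- At HR 0.6 (16.9 adaptive events) the same method gives 67.5%, against the stated 67%.

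The follow-up assumptions therefore reproduce the stated power. That power concerns time to discontinuation and is not affected by this point.

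**Is the OS median reached?** Kaplan-Meier curves were simulated with exponential times, equal arms and censoring uniform between 24 and 48 months (4,000 runs; repeat runs differ by about a point). The last column stops everyone at 24 months, where the chance is P(Bin(n, 1 − S(24)) ≥ n/2). Cells show conventional / adaptive.

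| Assumed median OS | Follow-up 24–48 months | Stopped at 24 months |
|---|---|---|
| 36 months | 68% / 72% | 26% / 13% |
| 48 months | 46% / 43% | 11% / 3% |
| 72 months | 22% / 14% | 2% / 0.1% |

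The 72-month row comes from the 56% figure under an exponential model: λ = −ln(0.56)/60 = 0.00966 per month, so the median is 0.693/0.00966 = 71.7 months.

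Actual OS follow-up may fall short of 24–48 months. Section 5.4.2 limits survival follow-up to 1 year after early discontinuation, while section 4.1 has survival follow-up after progression with no stated limit. The 24-month column illustrates the effect of shorter follow-up; it is not a claim about the design.

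**Is the PFS median reached?** Adaptive medians other than 24 are the published values doubled (HR 0.50).

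| Arm, true median PFS | Follow-up 24–48 months | Cut at 24 months |
|---|---|---|
| Conventional, 10.8–12 | about 100% | 99–100% |
| Conventional, 18.3 | 98% | 85% |
| Conventional, 30.5 | 80% | 38% |
| Adaptive, 21.6–22.4 | 98–99% | 68–72% |
| Adaptive, 24 | 97% | 58% |
| Adaptive, 36.6 | 71% | 12% |
| Adaptive, 61 | 23% | 1% |

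The 58% is exact: P(Bin(24, 0.5) ≥ 12) = 1 − 0.419 = 0.581.

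**Precision of a between-arm estimate.**
- PFS, medians 12 and 24: 0.50 × e^(±1.96 × 0.402) = 0.23 to 1.10.
- OS, median 72 in both arms: 3.5 + 7.0 = 10.5 expected deaths, SE √(1/3.5 + 1/7.0) = 0.654, so e^(±1.96 × 0.654) = 0.28 to 3.60 around HR 1.
- Response-rate difference, equal rates p: half-width about 1.96 × √[p(1 − p)(1/12 + 1/24)], which is 31 points at p = 0.28 and 35 points at p = 0.49.

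**The case against.** The best defence is that the trial calls itself a pilot phase 2 study, the objective is to evaluate and not to test, and section 4.2.2 describes the endpoints regimen by regimen. Per-arm estimates with intervals fit that wording. With 36 randomised patients any contrast will be imprecise, and an OS hazard-ratio interval of 0.28 to 3.60 settles nothing.

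Most of this stands as a reason to label the contrasts descriptive and to attach no significance claim. It does not justify leaving them out. The plan already accepts a log-rank PFS comparison on about 9 plus 12 patients, while acknowledging that the numbers are small. An interval of 0.23 to 1.10 also shows the imprecision openly, which two separate medians do not.

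Two stronger readings are tempting, and the documents support neither.

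- A reader might infer that the medians are mostly unreachable. For PFS this fails on the plan's own figures unless PFS is cut at 24 months or the median is long. A 24-month cut is a possible reading, because sections 6.1.8 and 7.3.3 place treatment after 24 months outside the protocol. However, section 10.4 assumes a minimum of 2 years after accrual, and section 7.3.3 continues imaging beyond cycle 24. For OS, the 72-month median needs an exponential model and a 56% figure that covers distant metastases in general. The trial enrols progressive, radioiodine-refractory DTC together with MTC, and its median OS could be much shorter.
- A reader might infer that the secondary objective goes unanswered and the randomisation is wasted. Per-arm estimates from randomised arms still permit an informal comparison. What is missing is the effect estimate and its interval.

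**Conclusion.** The concern holds in this form: the objective compares two regimens, and section 10.3.2 specifies no randomised between-arm estimate for response, PFS or OS. This rests on the text alone.

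The median is a fragile sole summary for OS. The chance of reaching it runs from about 70% per arm at an assumed 36-month median down to 22% (conventional) and 14% (adaptive) at 72 months, and it is lower if survival follow-up stops early. These figures assume exponential survival, equal arms and complete follow-up to 24–48 months. For PFS the median is usually obtainable, at about 97% for a 24-month adaptive median, so fragility there is conditional on a 24-month cut or a long adaptive median.

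This is a worthwhile improvement to the secondary analyses. It does not affect the primary endpoint or the stated power.

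**What to change.** In section 10.3.2, state that all secondary estimates are by randomised arm in all randomised patients, and add the following, labelled descriptive:

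1. PFS and OS hazard ratios with 95% CIs, stratified by DTC/MTC (the randomisation factor) if the event counts allow.
2. Kaplan-Meier PFS and OS rates at 12 and 24 months by arm, with the between-arm difference and 95% CI.
3. The response-rate difference with a Newcombe 95% CI, which builds on the Wilson intervals already planned.

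Keep the medians as descriptive summaries. Restricted mean time to 24 months is optional. Reconcile the survival follow-up in sections 4.1 and 5.4.2, and state whether PFS is counted beyond 24 months.

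The cost is protocol wording and a few more tables from data already collected, with no added patients or procedures. The downside is wide intervals, which the report should present as such.

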10.3.3 EXPLORATORY ANALYSES

- To determine a predictive biomarkers of TKI response

Exploratory analysis to assess the association of potential biomarkers with disease response will be made using logistic regression.

10.4 SAMPLE SIZE

The planned study is a randomized clinical trial, with 2:1 randomization to adaptive therapy versus conventional therapy. The primary endpoint is time-to-discontinuation (TTD) of treatment, which is a “survival analysis”-type statistical comparison. We plan to enroll 24 patients on the adaptive therapy and 12 on the conventional therapy arm. Assuming uniform enrollment of patients for 2 years, with a minimum follow-up of 2 years, and a one-sided $\alpha = 0.20$, we will have 82% power to detect a hazard ratio of 0.50, assuming 12 and 24 month median TTD for the conventional and adaptive therapy groups. If the median TTD of the adaptive group is 20 months (HR=0.6), the power is 67%.

We anticipate that 20% of the patients will not have the $\geq 50\%$ drop in tumor markers needed for study randomization arm of the study. Thus, we anticipate recruiting ~45 patients to have 36 patients for randomization.

Objective time-to-discontinuation criteria are described in Section 4.2.1. Patients may electively withdraw from treatment at any time and will be counted as a discontinuation event. All randomized patients will be included in the primary analysis. A sensitivity analysis will also be conducted, where the patients who choose to withdraw are considered as censored (non-events) at the time of withdrawal.

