Principal Investigator: [name] Print/Type Name

Signed: _____ Date: _____

STUDY SUMMARY

Title: Adaptive tyrosine kinase inhibitor therapy in patients with advanced progressive thyroid cancer.

Précis: This is a randomized phase II clinical trial to evaluate the efficacy and tolerability of tyrosine kinase inhibitor (TKI) therapy through adaptive (intermittent) versus conventional (continuous) dosing schedule in patients with differentiated thyroid cancer (DTC) or medullary thyroid cancer (MTC).

Objectives: **Primary objective:**

- To evaluate the efficacy and tolerability of TKI therapy (Lenvatinib or Sorafenib for DTC; Cabozantinib or Vandetanib for MTC) through adaptive (intermittent) versus conventional (continuous) regimen.

Secondary objective:

- To evaluate response and survival of TKI therapy (Lenvatinib or Sorafenib for DTC; Cabozantinib or Vandetanib for MTC) through adaptive (intermittent) versus conventional (continuous) regimen.

Exploratory objective:

- To determine predictive biomarkers of TKI response.

Endpoint: **Primary endpoint:**

- Time to TKI treatment discontinuation due to progressive disease, intolerability, or disease-related death at 2 years.

Secondary endpoints:

- Overall response rate
- Progression free survival
- Overall survival

Exploratory endpoints:

- Determine predictive biomarkers of TKI response

Population: Patients with advanced progressive 131I-refractory DTC or MTC will be enrolled to this study. Forty-five patients responding to TKI therapy (defined as $\geq 50\%$ drop in tumor marker level within the first two months of treatment) will be randomized to receive TKI therapy either through adaptive (intermittent) or conventional (continuous) regimen.

Phase: Randomized phase II clinical trial

Number of Sites enrolling participants: 1 (Moffitt Cancer Center)

Description of Study Agent:

[figure not shown]
- All patients will start receiving standard of care treatment: Lenvatinib 24 mg daily or Sorafenib 400 mg twice daily with DTC; Cabozantinib 140 mg daily or Vandetanib 300 mg daily with MTC. Doses will be adjusted as needed due to toxicity or drug tolerance in both arms.
- Patients in the conventional therapy regimen will receive continuous treatment at the indicated dose until disease progression or development of intolerability.

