All study participants will be followed for at least 24 months after treatment initiation. Patients will continue to receive treatment until confirmed disease progression, development of unacceptable toxicity, withdrawal of consent, or study termination by investigator. After disease progression, subjects will be followed for survival and may be treated according to standards of care, which includes conventional (continuous) TKI treatment for patients in the adaptive therapy arm.

After 24 months, patients in the adaptive therapy arm that remain on TKI therapy and under control will be given the choice to continue with adaptive therapy or to convert to conventional (continuous) regimen, which is the current standard of care.

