4.2 STUDY ENDPOINTS

4.2.1 PRIMARY ENDPOINT

The primary endpoint is time to TKI treatment discontinuation due to progressive disease, intolerability (Grade 3 and 4 toxicities refractory to best symptom management that are deemed probably or definitely related to study treatment only), or disease-related death at 2 years. We hypothesize that time on TKI treatment will be significantly longer for patients on the adaptive therapy arm than on the conventional therapy arm because we expect a decrease in drug-associated toxicities and a delay in the selection of resistant clones in the adaptive therapy arm.

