6.1.8 DOSE ADJUSTMENTS/MODIFICATIONS/DELAYS

All patients will start receiving standard of care treatment:

- DTC: Lenvatinib 24 mg daily or Sorafenib 400 mg twice daily
- MTC: Cabozantinib 140 mg daily or Vandetanib 300 mg daily.

Dose will be adjusted as needed due to toxicity or drug tolerance in both arms (See below).

- Patients in the conventional therapy regimen (“responders” and non-responders”) will receive continuous (daily) treatment at the indicated dose.

- Patients in the adaptive therapy regimen will receive TKI therapy in cycles: continuous (daily) treatment at the indicated dose until the patients’ tumor marker (thyroglobulin in DTC patients; calcitonin or CEA in MTC patients) drops by $\geq 50\%$ from the level at the time of enrollment (“baseline” level). Only tumor markers that meet inclusion criteria at baseline can be used for randomization and adaptive therapy purposes. A new cycle of TKI treatment will begin:

1. When/if the tumor marker increases to $\geq 70\%$ of the “baseline” level.

OR

2. At the discretion of the treating physician if a patient develops worsening disease-related symptoms with rising tumor marker levels indicating disease progression. In the case of resumption for disease-related symptoms, TKI treatment will continue until the symptoms improve at the discretion of the treating physician and the tumor markers are again $\leq 50\%$ from the level at the time of enrollment.

All study participants will continue to receive treatment until confirmed disease progression, development of unacceptable toxicity, withdrawal of consent, or study termination by investigator.

After disease progression subjects will be followed for survival and may be treated according to standards of care, which includes conventional (continuous) TKI treatment for patients in the adaptive therapy arm.

Held doses will be considered missed and will not be made up so that patients will complete on-study treatment within the anticipated 24 month duration. Treatment may be delayed for toxicity, other palliative treatments (i.e. palliative radiation, palliative surgery, etc.) for a maximum of 4 weeks. Any treatment beyond the 24 months specified herein will be considered off protocol and not subject to the requirements of this protocol.

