7.3.3 FOLLOW-UP

Follow-up Visits

Study participants will be seen weekly for the first cycle (Cycle 1 Days 8, 15 and 22), every two weeks for the second cycle (Cycle 2 Days 1, 15), every four weeks until cycle 12 (Day 1 of Cycles 3-12); and every 2 cycles thereafter until end of study (Day 1 of cycles 14, 16, 18, 20 and 24). However, when the patient is off the TKI with observation only in the adaptive arm, the patient needs to follow up every 28 days (+/- 7 days) for determination of starting a new cycle.

In each scheduled visit we will:

- Obtain vital signs.
- Record all concomitant medication use.
- Perform a comprehensive physical examination.
- Evaluate ECOG performance status.
- Obtain laboratory tests and urinary dipstick.
- Assess for AEs and SAEs.
- Assess compliance with the medication.
- Assess survival.

Thyroid panel evaluation

Thyroid panel will be assessed every 2 weeks during the first two cycles (Cycle 1 Day 15, Cycle 2 Day 1, Cycle 2 Day 15, and Cycle 3 Day 1). If the tumor marker (thyroglobulin in DTC patients; calcitonin or CEA in MTC patients) drops by $\geq 50\%$ from baseline (Cycle 1 Day 1) during the first two cycles (analysis of Cycle 3 Day 1 included), the patient will be randomized to receive either standard (continuous) or adaptive (intermittent) therapy. Patients randomized to

the standard therapy arm will then get Thyroid panel checked every 3 cycles (Day 1 of Cycle 6, 9, 12). Patients randomized to the adaptive therapy arm will get Thyroid panel checked every cycle (Day 1) during the first two years. After 24 months, patients in the adaptive therapy regimen who remain on TKI therapy will be given the choice to continue with the adaptive therapy regimen and monitoring of the thyroid panel in every cycle; or to convert to standard (continuous) regimen in which case thyroid panel evaluation will be checked every 3 cycles. In either case, all patients that continue to receive TKI therapy beyond 24 months will be treated off trial. Patients in which the tumor marker does not drop $\geq 50\%$ within the first two months of TKI therapy will be managed by the standard of care.

Diagnostic imaging

Diagnostic imaging of affected and suspected sites (CT and/or MRI) will be done at Day 1 of cycles 3, 6, 9, 12, 16, 20, 24 in all patients. Diagnostic imaging will continue to be done every 4 months thereafter while the patient remains on TKI therapy or as clinically indicated otherwise.

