7.3.5 EARLY TERMINATION VISIT

An End of Treatment (EOT) visit will be performed for all subjects who do not complete the 24 month treatment period for any reason (e.g. disease progression, unacceptable toxicity, withdraw consent, etc.). At the end of treatment (30 days after last TKI dose, or any time within 30 days of being removed from treatment for patients in the adaptive therapy arm) the following data will be collected:

- Obtain vital signs.
- Record all concomitant medication use.
- Perform a comprehensive physical examination.
- Evaluate ECOG performance status.
- Obtain laboratory tests and urinary dipstick.
- Assess for AEs and SAEs.
- Assess compliance with the medication.

- Assess survival.

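### The stated 82% power counts discontinuations up to month 48, but the endpoint is set at two years; a 24-month cut-off gives about 77%, and the plan does not define the window

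*Combined protocol and SAP*

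**What the plan says.** Section 10.4 (repeated in 10.1) plans 24 adaptive and 12 conventional patients, one-sided alpha 0.20, and median times to discontinuation of 12 and 24 months. It assumes: "Assuming uniform enrollment of patients for 2 years, with a minimum follow-up of 2 years". It states 82% power for HR 0.50, and 67% if the adaptive median is 20 months (HR 0.60). Section 10.2 repeats the 82%.

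The Study Summary defines the primary endpoint as "Time to TKI treatment discontinuation due to progressive disease, intolerability, or disease-related death at 2 years". Section 4.2.1 ends its definition in the same way: "or disease-related death at 2 years".

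For the period after month 24:

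- Section 6.1.8: "Any treatment beyond the 24 months specified herein will be considered off protocol and not subject to the requirements of this protocol".
- Section 7.3.3: "all patients that continue to receive TKI therapy beyond 24 months will be treated off trial".
- Section 4.1: adaptive patients who remain on therapy and under control "will be given the choice to continue with adaptive therapy or to convert to conventional (continuous) regimen".
- Section 7.3.5: "An End of Treatment (EOT) visit will be performed for all subjects who do not complete the 24 month treatment period".
- Section 7.3.3 lists clinic visits to the end of the study, the last at cycle 24.

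Other text allows longer observation. The Summary gives a participant duration of 48 months, Section 4.1 sets follow-up at 24 months or more, Section 7.3.3 continues imaging every four months for patients still on TKI, and Section 7.3.4 places the final visit at 24 months or later.

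Sections 4.2.1 and 10.4 name no time origin. Section 10.3.1 counts from the start of TKI, but for a different analysis: Fisher's exact test on 12-month status.

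**The concern.** The power calculation and the endpoint appear to use different observation windows. The calculation needs discontinuations between months 24 and 48. The endpoint wording stops at two years, and the conduct sections treat what follows as outside the trial. The two-year wording is not an explicit censoring rule, and nothing says whether a discontinuation in month 30, for example, is a primary event. Two statisticians working from this text could build different primary datasets, and the choice could be made after results are known.

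The late events are also the hardest to interpret. Under the design assumption about half of the adaptive arm reaches month 24 without an event, and those patients are then offered the control regimen. Events after a switch no longer compare adaptive with continuous dosing.

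A separate slip concerns the sample size. The Summary says that forty-five responders will be randomized, while 10.1 and 10.4 say about 45 recruited and 36 randomized.

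**Working it through.** **Inputs (Section 10.4).** 12 conventional and 24 adaptive patients; medians 12 versus 24 months (HR 0.50) or 20 months (HR 0.60); one-sided alpha 0.20 (z = 0.842); uniform accrual over 24 months plus at least 24 months of follow-up. Assumed: exponential times and no separate loss rate, since none is given.

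**Event probabilities.** With hazard λ = ln 2 / median:

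- Follow-up uniform on 24 to 48 months: p = 1 − (e^(−24λ) − e^(−48λ)) / (24λ)
 - Median 12: 1 − (0.250 − 0.0625)/1.386 = 0.865
 - Median 24: 1 − (0.500 − 0.250)/0.693 = 0.639
 - Median 20: 1 − (0.435 − 0.189)/0.832 = 0.704
- Cap at 24 months: p = 1 − e^(−24λ) = 0.750, 0.500 and 0.565

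**Expected events.**

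- 24 to 48 months: 10.4 + 15.3 = 25.7 (HR 0.50); 10.4 + 16.9 = 27.3 (HR 0.60)
- 24-month cap: 9.0 + 12.0 = 21.0 (HR 0.50); 9.0 + 13.6 = 22.6 (HR 0.60)

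At HR 0.50 the events after month 24 are 12 × (0.865 − 0.750) = 1.4 conventional and 24 × (0.639 − 0.500) = 3.3 adaptive. The total of 4.7 is 18% of 25.7.

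**Reproducing the stated power.** Using Φ(|ln HR| / √(1/d₁ + 1/d₂) − 0.842):

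- HR 0.50: 0.693/√(1/10.38 + 1/15.34) = 1.725, so power is Φ(0.883) = 81.1%
- HR 0.60: 0.511/√(1/10.38 + 1/16.91) = 1.295, so power is Φ(0.454) = 67.5%

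Both agree with the stated 82% and 67%. Reading alpha 0.20 as two-sided gives 65–70% and 49–53%, which does not.

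**With the cap.**

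- HR 0.50: 0.693/√(1/9 + 1/12) = 1.572, so power is Φ(0.730) = 76.7%
- HR 0.60: 0.511/√(1/9 + 1/13.55) = 1.188, so power is Φ(0.346) = 63.5%

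**Other methods.**

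| Method | HR 0.50, 24–48 months | HR 0.50, cap 24 | HR 0.60, 24–48 months | HR 0.60, cap 24 |
|---|---|---|---|---|
| Simulated log-rank, 1,000,000 runs | 81.1% | 76.8% | 67.7% | 63.9% |
| Freedman | 82.9% | 78.2% | 69.2% | 64.8% |
| Schoenfeld | 79.3% | 74.4% | 66.1% | 61.9% |

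No capped figure is within 2 points of the stated value.

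**Conversion at month 24 (assumption).** The expected number of adaptive patients without an event at month 24 is 24 × 0.500 = 12.0 (HR 0.50) or 24 × 0.435 = 10.4 (HR 0.60). The plan gives no conversion rate. The simulation keeps the 24 to 48 month window and moves converters to the control hazard at month 24:

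| Converting | HR 0.50 | HR 0.60 |
|---|---|---|
| 0% | 81.1% | 67.7% |
| 25% | 79% | 66% |
| 50% | 76.8% | 64.1% |
| 100% | 71.9% | 60.4% |

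**Time origin.** Randomization follows the marker checks, on Days 15, 29, 43 or 57. If the clock starts at randomization but observation ends 24 months after TKI start, power is 76.1% and 63.2% with randomization spread evenly over those days. It is 75.5% and 62.8% in the worst case of 22 months for everyone.

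**The test in 10.3.1.** On-treatment probabilities at 12 months are 0.500 versus 2^(−12/24) = 0.707 or 2^(−12/20) = 0.660. Exact enumeration of Fisher's test at one-sided 0.20, without historical controls, gives 52.1% and 39.8%.

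**The case against.** The longer window has real support. Two years of accrual plus two of follow-up equals the 48-month study duration. Section 6.1.9 continues therapy to progression or toxicity without a 24-month limit, and footnote n of Table 8 ties the end-of-treatment visit to the last dose. Sections 6.1.8 and 7.3.3 put later treatment off trial, but do not say that event collection stops. The last listed visit, Cycle 24 Day 1, is day 23 × 28 + 1 = 645, about 21 months, so it does not mark a 24-month end either. All of this stands. It shows that later observation is not ruled out, which is why the point is an undefined window and not a proven cap. None of these places says whether a late discontinuation counts. Section 7.3.5 limits the end-of-treatment visit to those who do not complete 24 months, which sits uneasily with footnote n.

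The loss is also modest for a trial that calls itself a pilot and uses one-sided alpha 0.20. The choice of formula alone moves the uncapped figure from 79.3% to 82.9%. This limits the weight of the point. But within any one method the cap still costs 4 to 5 points at HR 0.50, and the interpretation of events after a switch is a matter beyond power.

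The conversion model is an assumption: converters take the full control hazard at once, and at 25% conversion the longer window still has the advantage. That is fair, and the whole range is therefore shown.

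Finally, the 12-month Fisher test is the only primary test specified, and if it is kept the window question falls away. That is correct, so it has to be settled first. Even then the 82% would not describe that test.

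**Conclusion.** The concern holds. The stated 82% and 67% are arithmetically right, but only if discontinuations up to month 48 count. The endpoint wording and the off-trial text point to two years, other sections point beyond it, and no rule decides between them. With a 24-month cap, power is about 77% (21.0 events) and 64% (22.6 events). Within a method the loss is 4 to 5 points at HR 0.50 and about 4 points at HR 0.60. Without a cap, the stated power also requires that conversion at month 24 leaves the hazard unchanged. At 50% conversion to the control hazard the gain over the cap is gone, and at 100% power is lower than with the cap. These figures rest on exponential times, no separate losses and, for conversion, assumed rates. This should be corrected before analysis. The mismatch between forty-five and 36 randomized patients is a plain contradiction, but it is independent of the window.

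**What to change.** First reconcile Section 10.3.1 with 10.4, because neither 82% nor 77% describes Fisher's test at 12 months. If a log-rank analysis is kept, state the time origin in 4.2.1 and 10.4 and choose one of two windows.

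- **Option A**, the better fit to the endpoint wording and the off-trial text: censor patients without a discontinuation event at 24 months in the primary analysis. Restate the power in 10.1, 10.2 and 10.4 as about 77% (HR 0.50, about 21 events) and, where HR 0.60 is given, 64% (about 22.6 events).
- **Option B**: remove the two-year limit from the endpoint. State that the date and reason of discontinuation are still collected after month 24 for patients treated off trial, and how conversion to the continuous regimen is handled in the analysis. The 82% and 67% can then stay, with the assumption beside them that conversion does not change the hazard.

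Both options decide which events the analysis counts, not how long patients are treated. Correct the Study Summary to about 45 enrolled and 36 randomized.

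The cost is one design decision and wording in the Study Summary and Sections 4.2.1, 10.1, 10.2 and 10.4. Option A lowers the stated power by the amounts above. Option B adds data collection after month 24. Neither needs more patients.
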